The primary observation to be made is the level of PaCO₂ in the arterial blood, specifically when the patient is insufflated and deflated during the surgery. As a result of the consistent pressure that the AirSeal® system maintains, CO₂ will be absorbed in lower levels when compared to the standard of care systems in which fluctuations in intra-peritoneum pressure are seen. Therefore, higher pressures will result in higher levels of CO₂ exchange in the blood, leading to increased vasodilation and lower pH levels.⁸ Given the potential benefit of using valve-less trocars during robotic prostatectomies as demonstrated in other laparoscopic abdominal procedures, the aims of this study are:

Aim #1) Describe the perioperative CO₂ absorption rates between the conventional and valve-less trocar groups via the end-tidal CO₂ and PaCO₂, at baseline, 60 minutes intraoperatively, and immediately following surgery. Optimal intraoperative levels for PaCO₂ and end tidal CO₂ should be between 33-37 mmHg. These values are expected to slowly rise throughout surgery due to CO₂ absorption. The anesthesiologist will make specific adjustments and alter ventilation settings throughout the surgery to prevent the values from elevating further once they reach 37-38 mmHg. Between 33-36 mmHg, no adjustments are made. Therefore, we will also examine the valve and valve-less trocar groups on their ability to maintain acceptable arterial blood gas (ABG) levels by comparing the number of interventions required by the anesthesiologist during the procedure between groups.

Aim #2) Compare the maximum intraoperative pneumoperitoneal pressure (mmHg), smoke evacuation quality (categorical), and overall operative times (minutes) between the conventional and valve-less trocar groups.

Aim #3) Compare pain scores through discharge from the preoperative and post-anesthesia care units (PACU) by monitoring self-reported pain ratings using an 11-point numerical rating scale (NRS-11) and pain medication usage via morphine equivalent dose (MED) units.

Table 1. Definitions of key variables.

Variable	Definition	Unit
CO ₂ absorption rate	Not directly measurable. We are using end tidal CO ₂ and PaCO ₂ to indirectly measure the absorption rate.	N/A
Arterial Blood Gases (ABGs)	Measurement of the pH level and the bicarbonate, oxygen, and carbon dioxide concentrations in arterial blood (HCO ₃ , PaCO ₂ & PaO ₂); important in diagnosis of	N/A

	many respiratory diseases.	

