Exclusion criteria to participation in this study include:

- 5) Age < 18
- 6) Emergency surgery
- 7) Persons not capable of providing informed consent
- 8) Persons participating in any other research study involving an investigational drug or device or investigational surgical procedure that could interfere with the physiologic parameters being collected (for example, a study evaluating different anesthesia regimens that could confound study results).
- 9) Non English-speaking

2.2 - Hypothesis

It is hypothesized that the AirSeal® System will allow for lower CO₂ absorption rates than the Xcel® System. Furthermore, lower variance in pneumoperitoneal pressure will allow for less "over-pressure" events and peritoneal stretch, which may reduce postoperative pain. Pain will therefore also be assessed through self-report and post-operative pain medication usage (see Table 4 & Appendix A), and analyzed in comparison between both groups.

The term "over pressure" refers to times when the measured pressure in the peritoneal cavity exceeds the set pressure on the insufflator. In such cases, the standard insufflation systems will stop the flow of CO₂ into the abdomen through the port and will actively vent gas to reduce the pressure back to the set point (usually 10mmHg with a maximum of 20mmHg). This "over pressure" theoretically should not occur with the AirSeal® system because the lack of a valve on the port allows gas to escape immediately when the pressure rises (e.g. abdominal muscle contractions when anesthesia is light) so that the pressure does not exceed the set level. "Peritoneal stretch" refers to stretching of the peritoneum (lining of the abdominal wall) from insufflation of the abdomen. The higher the pressure of the pneumoperitoneum/intra-abdominal pressure, the more stretch there will be of the peritoneum with potentially more postoperative pain.

We intend to analyze the results of a total of 100 patients randomized to either the AirSeal® system or conventional trocars.

2.3 - Study Variables & Outcomes of Interest

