The following data points are all routinely collected for patients who choose to undergo robotic prostatectomy, via the OhioHealth electronic medical record, CareConnect. We will collect similar data points for patients electing enrollment in this trial which include the following listed below (Tables 2-4). Data points which are not collected in the standard of care setting are noted below in **bold face type**. Only the study staff will have access to the database created solely for use in this study. Data will be de-identified following study completion, prior to statistical analysis.

Table 2. Study Variables by Operative Time-point

(a) Preoperative data [collected at the preoperative office/clinic visit, in the office setting, or in

the pre-anesthesia testing (PAT) office visit]:

- 1) Medical record number
- 2) Patient name
- 3) Patient date of birth
- 4) Phone number
- 5) Email address
- 6) Body mass index (BMI)
- 7) Weight (lb)
- 8) Medical history
- 9) Surgical history (major only)
- 10) Serum creatinine (most recent prior to surgery) (mg/dl)
- 11) Hemoglobin (g/dl)
- 12) Preoperative pain measured by the NRS-11 (Appendix A)**

(b) Intraoperative data:

- 1) Details of the surgical procedure
- 2) The number, size(s), and locations of ports used (standard protocol vs. deviation from standard protocol)
- 3) Values obtained from anesthesia report at baseline, 60 minutes after insufflations, and at the end of procedure and mean and standard deviation calculated from continuously recorded values:
 - a) End tidal CO₂ (mmHg)
 - b) O₂ saturation (%)
 - c) Respiratory rate
 - d) Blood pressure
 - e) Heart rate
 - f) Tidal volume (ml)
 - g) PIP (peak inspiratory pressure) (mmHg)
 - h) PEEP (positive end-expiratory pressure) (mmHg)
- 4) CO₂ absorption rate via arterial blood gases (ABGs) at baseline, 60 minutes after insufflations, and at the end of the procedure [PaCO₂ (mmHg), HCO₃ (mmol/L) & PaO₂ (mmHg)]
- 5) Number of times the anesthesiologist intervenes to adjust ventilation settings throughout the surgery to prevent the values from elevating further once they reach 37-38 mmHg
- 6) Estimated blood loss (EBL, in ml)
- 7) Core body temperature (after trocar placement, at 30 minutes, at 60 minutes, and at end of procedure; Fahrenheit)
- 8) Insufflation time (minutes)

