For item (b)3, continuous values will be exported into individual patients-specific Excel spreadsheets with the assistance of the CareConnect Systems Analysts. This is due to the fact that there are far too many data points (ET CO₂, O₂ saturation, RR, BP, HR, TV, PIP, PEEP, every 1 minute for 120 minutes) to be manually extracted and subsequently manually entered into the Data Collection Tool by study staff. The biostatistician will perform individual analyses on these data sets, and calculate means and standard deviations to be entered into the Data Collection Tool.

For item (d)4, we are evaluating for oliguria in the immediate post-operative period (1900-0700 hours). Oliguria is infrequently viewed as a complication of laparoscopic surgery. The rate of urine output in

healthy patients undergoing laparoscopic surgery is measured during the period of CO₂ pneumoperitoneum and for several hours after desufflation. For patients that are discharged prior to the completion of the urine output collection (i.e., prior to 0700 hours postoperatively), they will be instructed to take home their urine collection canister and collection instructions to complete measurements following discharge. The Research Coordinator will then call the patient the following morning for the urine output measurement.

Table 3. Arterial Blood Gases (ABGs) monitoring schedule by anesthesiologist.

Timepoint	Definition
Baseline	At insertion of the catheter
60 minutes	60 minutes after insufflations
End of the procedure	Immediately at the end of surgery

We will be measuring the trend in arterial blood gases over time (Table 3). Optimal intraoperative levels for PaCO₂ and end tidal CO₂ should be between 33-37 mmHg. These values are expected to slowly rise throughout surgery due to CO₂ absorption. The anesthesiologist will make specific adjustments and alter ventilation settings throughout the surgery to prevent the values from elevating further once they reach 37-38 mmHg. Between 33-36 mmHg, no adjustments are made.

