Since the anesthesiologist will be adjusting ventilator settings at 37-38 mmHg to typically keep the end tidal CO₂ below 40 mmHg, we expect that there will not be a large amount of difference between standard and valve-less trocars regarding the ABGs. However, the ABGs will change over time, warranting the alteration of ventilator settings by the anesthesiologist. In other words, if the ABGs are same between the two groups but the anesthesiologist had to increase the respiratory rate or tidal volume to keep end tidal CO₂ low more so in the standard group than the valve-less, then we will conclude that the valve-less was better. Essentially, the ABGs are a sort of "control" whereby even if they are not different, it still allows us to know whether or not there was a real physiologic difference occurring, whether or not we saw a difference in the other measures that were adjusted in real time.

Table 4. Pain monitoring schedule by Pre-op and PACU RNs using NRS-11.

Timepoint	Definition
Baseline	Prior to surgery
Post-operatively	After surgery & after anesthesia completion
30 minutes post-operatively	30 minutes after surgical completion time (+/- 5 minutes)
60 minutes post-operatively	60 minutes after surgical completion time (+/- 5 minutes)
At discharge	Immediately prior to discharge from the PACU

Postoperative (post-anesthesia) pain will be evaluated at baseline, post operatively, once every thirty minutes for the first hour and every 8 hours until discharge (Table 4). Floor nurses (preoperative and PACU) will record pain scores reported by patients during structured interviews using an 11-point numerical rating scale (NRS-11), in which a rating of 0 corresponds to no pain, ratings of 1-3 indicate mild pain, 4-6 indicate moderate pain, and ratings of 7-10 correspond to severe pain (Appendix A).

Data will be collected using the forms in the Appendix. Data will be collected by a member of the research team (clinic nurse or clinical research coordinator). All data will be coded by subject number and de-identified. The designated clinical research coordinator will hold the key to subject codes in a locked cabinet and password-protected electronic file. Case reports formed with the coded key will be available only to the study staff.

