- General or specific changes in the subject's condition that render further treatment unreasonable or unsafe within the standards of clinical practice in the judgment of the Principal Investigator or treating physician

2.5 – Statistical Analysis

We will first compare the demographic and pre-operative clinical characteristics of the conventional and valve-less trocar groups to evaluate randomization fidelity. If any characteristics are found to be statistically significant between the groups, this will be accounted for in the analyses of the primary and secondary outcomes. We will describe all categorical variables as percentages and continuous variables with means and standard deviations.

Aim #1) Describe the perioperative CO₂ absorption rates between the conventional and valve-less trocar groups via the end-tidal CO₂ and PaCO₂ , at baseline, 60 minutes intraoperatively, and immediately following surgery. We will also examine the valve and valve-less trocar groups on their ability to maintain acceptable ABG levels by comparing the number of interventions required by the anesthesiologist during the procedure between groups.

We will describe the change in CO₂ and PaCO₂ levels at 3 intervals: baseline to 60 minutes, 60 minutes to end of surgery, and baseline to end of surgery to examine the trends in both groups. We will compare the conventional and valve-less trocar groups on the number of interventions required by the anesthesiologist to maintain acceptable pressure using Poisson regression. If a significant number of patients required no intervention we will use a zero-inflated model. Statistical significance will be set at p<.05. We will also compare CO₂ absorption rates between high pressure (>8mmHg) and low impact (≤8mmHg) procedures.

Aim #2) Compare the maximum pneumoperitoneal pressure (mmHg), smoke evacuation quality (categorical), and overall operative times (minutes) between the conventional and valve-less trocar groups.

We will compare the conventional and valve-less trocar groups on maximum pneumoperitoneal pressure and overall operative time using t-tests or Wilcoxon rank sum tests. We will compare the groups on evacuation quality using a chi-square test. Statistical significance will be set at p<.05.

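### Aim #1 plans no between-arm estimate or interval for PaCO2 or end-tidal CO2, and section 2.5 does not directly evaluate the section 2.3 rule for calling the valve-less trocar better

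*Combined protocol and SAP*

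**What the plan says.** Section 1.2 (Specific Aims/Rationale) states: "The primary observation to be made is the level of PaCO₂ in the arterial blood". Section 2.2 (Hypothesis) gives a direction: "It is hypothesized that the AirSeal® System will allow for lower CO₂ absorption rates than the Xcel® System".

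For Aim #1, section 2.5 (Statistical Analysis) says: "We will describe the change in CO₂ and PaCO₂ levels at 3 intervals". The intervals are baseline to 60 minutes, 60 minutes to end of surgery, and baseline to end of surgery. The stated purpose is to look at trends in each group, and continuous variables are summarised by means and standard deviations. The one between-arm test named in Aim #1 is a Poisson (or zero-inflated) regression on a count, defined in Table 2(b)5 of section 2.3 as "Number of times the anesthesiologist intervenes to adjust ventilation settings throughout the surgery".

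After Table 3, section 2.3 explains that ventilation is adjusted in real time, that little difference in blood gases is therefore expected, and that the gases serve as a kind of control. It then sets a rule for interpretation: "if the ABGs are same between the two groups but the anesthesiologist had to increase the respiratory rate or tidal volume", more so in the standard group, "then we will conclude that the valve-less was better".

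Respiratory rate and tidal volume are recorded at baseline, 60 minutes after insufflation and end of procedure (Table 2(b)3). They are also exported "every 1 minute for 120 minutes" and reduced to a mean and SD for each patient.

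**The concern.** The quantity named as primary has no planned contrast between the randomised arms, while Aims #2 and #3 name t-tests or rank tests, a chi-square test and a mixed model.

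The section 2.3 rule has two conditions, and section 2.5 evaluates neither directly. Blood gases being 'same' has no criterion and no interval behind it. A greater rise in respiratory rate or tidal volume in the standard arm has no named between-arm comparison. The intervention count bears on the second condition but is coarse: one large, sustained change counts the same as one small, brief one.

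The two conditions also depend on each other. Fewer interventions in one arm could reflect less CO2 absorption, or a higher CO2 that was tolerated. A between-arm PaCO2 estimate is what separates these readings. Without it, the favourable conclusion could be drawn from parallel descriptions and a count.

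**Working it through.** **Reading the sections together**

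| Element | Where stated | Between-arm analysis in 2.5 |
|---|---|---|
| PaCO2, primary observation | 1.2 | None; change described by arm |
| End-tidal CO2 | 1.2, Aim #1 | None; change described by arm |
| Blood gases 'same' | 2.3, after Table 3 | None; no criterion or interval |
| Respiratory rate or tidal volume raised more in standard arm | 2.3, after Table 3 | None named |
| Number of ventilation interventions | 2.3, Table 2(b)5 | Poisson or zero-inflated regression |

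The only other CO2 comparison in Aim #1 is by insufflation-pressure class (above 8 mmHg against 8 mmHg or less), not by randomised arm. The general statement that imbalances will be accounted for in analysing the primary and secondary outcomes does not supply a PaCO2 contrast. A figure after Aim #3 is not visible in the text available, and nothing is inferred from it.

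**What an interval would show**

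The plan's only size figure is 100 patients in total (section 2.2). It comes with no effect size, SD or power, so it cannot be reproduced. The following are assumptions: 1:1 allocation (50 per arm), two-sided 95% intervals, one time point, and a PaCO2 SD of 3, 4 or 5 mmHg.

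- Standard error of the difference: sqrt(2/50) = 0.200 SD.
- 95% half-width, unadjusted: t(0.975, 98 df) × 0.200 = 1.984 × 0.200 = 0.397 SD. For SDs of 3, 4 and 5 mmHg this is 1.2, 1.6 and 2.0 mmHg. The normal quantile gives 0.392 SD.
- 95% half-width, adjusted for baseline with assumed correlation r = 0.5: 0.397 × sqrt(1 − 0.5²) = 0.344 SD, or 1.0, 1.4 and 1.7 mmHg.

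**Why a non-significant test would not establish 'same'**

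With the same 50 per arm, the chance that a true difference of d SD gives p ≥ 0.05 is approximately Φ(1.960 − d/0.200):

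- d = 0.2: Φ(0.96) = 0.83
- d = 0.3: Φ(0.46) = 0.68
- d = 0.4: Φ(−0.04) = 0.48

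A true difference of 0.4 SD (1.2 to 2.0 mmHg over the assumed SDs) would be missed about half the time. The plan does not say that it would read 'same' this way. The figures show why the interval should be used.

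**The case against.** The strongest reply is that description is a reasoned choice. Because ventilation is adjusted to hold CO2 in range, PaCO2 is expected to differ little, and the informative outcome is how often the anesthesiologist had to act, which is tested. Aim #1 is worded as descriptive in both 1.2 and 2.5, and the section 2.3 sentence is explanatory prose rather than a formal decision rule. This stands as a reason to keep the count test and not to demand a formal equivalence test. It does not remove the need for an estimate, because the same passage rests a favourable conclusion on the gases being the same.

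Some stronger readings are tempting but not supported:

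- *A reader could never recover a baseline-referenced PaCO2 difference.* By-arm means and SDs of levels and of change would give both an unadjusted difference and a difference in change from baseline. The gap is that the plan neither estimates this nor uses it to support its conclusion.
- *The plan has no measure of how much ventilation changed, or ignores ventilation.* Respiratory rate and tidal volume are collected at three time points and by the minute, and would be described. What is missing is a named between-arm comparison.
- *The 120-minute export prevents a comparison in long cases.* Only the minute-by-minute average is limited; end-of-procedure values are collected separately.
- *A prespecified margin is indispensable.* The documents give no basis for one. The range in "Optimal intraoperative levels for PaCO₂ and end tidal CO₂ should be between 33-37 mmHg" is a target for individual patients, not a tolerance for a difference between arm means.

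**Conclusion.** The point holds as a cheap improvement. Section 2.5 plans no between-arm estimate or interval for the primary observation, and it evaluates the section 2.3 conclusion only through an intervention count that is valid but coarse. A reader might infer that the trial cannot answer its question or that the count test is unsound. The documents support neither: the comparison is randomised and the data needed are collected.

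The expected precision is a half-width of about 0.40 SD (1.2 to 2.0 mmHg), or about 0.34 SD (1.0 to 1.7 mmHg) with baseline adjustment. These figures rest on 50 analysed patients per arm, an SD of 3 to 5 mmHg and, for the adjusted figure, r = 0.5, none of which is given in the documents. The textual finding does not depend on them.

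**What to change.** In section 2.5, Aim #1:

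(a) Report the between-arm difference in PaCO2, and in end-tidal CO2, at 60 minutes and at end of surgery with 95% confidence intervals. Use a model with arm, time, arm-by-time and the baseline value, allowing for repeated measurements on the same patient. Keep the by-arm descriptions.

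(b) Keep the intervention-count test. Add a between-arm comparison of respiratory rate and tidal volume, using either the baseline, 60-minute and end-of-procedure values or the mean over the exported minutes. Name the one ventilation comparison that carries the section 2.3 conclusion and call the others supportive, so that no unranked set of tests is added.

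(c) State that 'same' will be judged from the PaCO2 confidence interval, not from by-arm description or a non-significant p-value. A margin fixed before the data are seen is optional.

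The cost is SAP wording and a little more analysis of data already collected. The sponsor must accept that the interval may be too wide to support 'same'. If the minute-by-minute average is chosen in (b), it covers only the 120 exported minutes.

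### The intervention count is tested by plain Poisson regression with no dispersion allowance, and the zero-inflated fallback lacks a trigger, family, tested coefficient and reported effect

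*Combined protocol and SAP*

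**What the plan says.** Section 2.5, Aim #1 sets out to assess how well each trocar type keeps blood gases acceptable by "comparing the number of interventions required by the anesthesiologist during the procedure between groups". The method is given as "using Poisson regression. If a significant number of patients required no intervention we will use a zero-inflated model", with significance at p<.05. Table 2(b) in section 2.3 defines the outcome as "Number of times the anesthesiologist intervenes to adjust ventilation settings throughout the surgery" to stop values rising once they reach 37-38 mmHg. Section 2.3 adds "Between 33-36 mmHg, no adjustments are made".

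Section 2.2 plans to "analyze the results of a total of 100 patients randomized to either the AirSeal® system or conventional trocars". No section gives an expected count, its variance, an expected share of patients without intervention, or an allocation ratio. No section mentions overdispersion or underdispersion, robust or scaled standard errors, or negative binomial regression.

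**The concern.** There are two separate gaps.

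**The Poisson step.** The model-based standard error assumes that variance equals mean. If patients differ in how often they need adjustment, for instance because case length varies, the p-value is too small and the interval too narrow. If counts are more regular than Poisson, the test is conservative. One surgeon, a standardized anesthesia regimen (both section 2.4) and a common adjustment range could push in that direction.

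**The fallback.** A zero-inflated model has two parts: one for patients who cannot need adjustment, and one for the count among the rest. The plan does not say how many zeros trigger the switch, which count distribution is used, whether arm enters both parts, or which coefficient or joint test carries the comparison. The Poisson ratio compares mean counts over all patients. A count-part ratio compares only patients able to need adjustment. If that coefficient alone were tested, a device benefit that spares some patients any adjustment would not be seen.

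This is the only Aim #1 outcome with a named between-arm test and threshold, so a reader should know beforehand what its p-value refers to.

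**Working it through.** **Inputs.** From the documents: 100 patients (section 2.2) and significance at p<.05 (section 2.5). Assumed: two-sided testing, 50 per arm, mean counts 0.5 to 4, and variance/mean φ from 0.7 to 3. The plan states no power, effect or error calculation for this outcome, so there is no figure of its own to reproduce.

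**1. Error of the plain Poisson test.** Under no difference, the Wald statistic has variance φ rather than 1, so the actual two-sided error is 2 × [1 − Φ(1.96/√φ)].

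| φ | 1.96/√φ | Actual error |
|---|---|---|
| 0.7 | 2.34 | 1.9% |
| 1.0 | 1.96 | 5.0% |
| 1.5 | 1.60 | 11.0% |
| 2.0 | 1.39 | 16.6% |
| 3.0 | 1.13 | 25.8% |

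Simulation used gamma-Poisson counts for φ>1, Poisson for φ=1 and binomial for φ<1. Over means 0.5 to 4 it gives about 2/5/11/16/25%.

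**2. Dispersion-adjusted errors on the same data.** Quasi-Poisson gives 4.2-5.2% throughout. Small-sample-corrected robust errors give 4.1-6.8%. At means 2 to 4 the robust range is 4.7-5.5%. The 6-7% values occur at means of 1 or less with φ=3.

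**3. How often the fallback is used.** The zero share of a pure Poisson count is exp(−mean): 61% at mean 0.5, 37% at 1, 14% at 2 and 2% at 4.
- Mean 1, φ=1: triggers of 10% and 20% zeros fire in 100% of trials, and 30% in 94%.
- Mean 2, φ=2 (25% zeros on average): if the model switches when zeros exceed 20/25/30%, it does so in 86/44/10% of trials.

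Within plausible ranges, the meaning given to the undefined phrase can therefore decide which model is used.

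**4. Error after a switch.** With null gamma-Poisson counts at mean 2, the zero-inflated Poisson count coefficient rejects 12-14% at φ=2 and 22-23% at φ=3. The whole two-step procedure at φ=2, with the three triggers above, rejects 13-16%. A zero-inflated negative binomial, which the text also permits, gives 5-8% for the count part and 3-6% for the joint test (500 trials per setting, simulation error about 1 point).

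**5. Which effect is estimated.** Suppose 30% (standard) and 50% (AirSeal) of patients can need no adjustment, and the rest have a mean of 3 in both arms.
- Ratio of mean counts, all patients: (0.50 × 3)/(0.70 × 3) = 1.5/2.1 = 0.71.
- Count-part ratio with arm in both parts: 3/3 = 1.00.

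The same data can therefore yield a reduction of about 29% or no difference, depending on what is reported after a switch.

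**6. Power of the alternatives.** Each range or triplet covers count means 2, 3 and 4.
- Benefit only in the zeros (20% vs 50% unable to need adjustment): count coefficient alone about 5%; robust or quasi-Poisson ratio of means 49-66%; joint two-part test 66-81%; comparison of the proportions with zero 76-88%.
- Every patient's mean falls by 30%: robust ratio of means 62/80/90%; joint two-part test 47/66/80%.

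Neither approach has more power in both cases.

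**The case against.** **The fallback is itself an allowance.** This stands in part. A zero-inflated model absorbs extra variance that comes from excess zeros, and the negative binomial form comes close to nominal. But it does nothing for underdispersion, its Poisson form still over-rejects when non-zero counts are overdispersed, and the plan does not choose between the forms.

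**A reader might infer that the Poisson test is anti-conservative here.** The documents do not support that. They give no mean or variance, and features of the design could reduce variation between patients as easily as case length could increase it.

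**A reader might also infer that the zeros seen will settle which effect is reported.** The text does not go so far. It never says that a zero-inflated coefficient is the reported effect, and an overall ratio of means can be derived from a two-part fit. What can be said is that the effect after a switch is not stated.

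**A third tempting reading is that the trial's conclusion hangs on this p-value.** Section 1.2 says "The primary observation to be made is the level of" PaCO₂, and Aim #1 is framed as descriptive. The rule in section 2.3 for judging the valve-less trocar better asks whether the anesthesiologist had to "increase the respiratory rate or tidal volume to keep end tidal" CO₂ low more often in the standard group. That is close to this count, but the rule names neither the count nor its test.

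**The remedy is partly a preference.** This also stands. Fixing the trigger, the family and a joint test would cure the lack of specification too.

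**Conclusion.** The point holds as a specification gap that should be closed; it is not a demonstrated error in the result. The Poisson step keeps its 5% level only when variance equals mean. Over the assumed range its actual level runs from about 2% to 25%, in a direction the documents do not allow one to predict. The fallback mitigates part of this, but it is too loosely described to be counted on, and it leaves open which effect the p-value would concern. All percentages rest on assumed means, dispersion and an equal split of the 100 patients, and so show sensitivity rather than forecast. If mean counts are 1 or less, the fallback would probably become the working analysis, and its missing specification would matter more than the Poisson standard error.

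**What to change.** In section 2.5, Aim #1, name one primary comparison that does not depend on the zeros seen: the ratio of mean counts per procedure by arm, from Poisson regression with quasi-Poisson standard errors (or small-sample-corrected robust ones), with 95% CI. Quasi-Poisson held its level better at low means. As a supporting result, report the proportion of patients needing no adjustment by arm, with 95% CI. If a zero-inflated model is kept, state its role, its count family and a joint test of both parts in advance.

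The same paragraph should say how section 2.5's rule on significant baseline differences applies to this model. It should also say how a count enters when data recording stops after an AirSeal malfunction (section 2.4). An analysis with log insufflation time as offset is optional and supporting only, because that time arises after randomization.

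**Cost.** Wording only, since the count is already collected. Interval widths on the log scale change by about √φ: √0.7 = 0.84, √1 = 1, √1.5 = 1.22, √2 = 1.41, √3 = 1.73. Almost nothing is lost if counts are Poisson. Against a joint two-part test, power is lower if the benefit lies only in the zeros; the supporting proportion covers that case.
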